8.3.2 Part 2 (Week 40 to Week 80)

For the exploratory efficacy analyses for Part 2, treatment groups are defined identically to that for the secondary efficacy analyses for Part 2. See Section 8.2.2.

The exploratory efficacy analyses are pre-specified as follows:

• Change in the MDS-UPDRS Part III total score, compared between the early and delayed groups at 76 weeks.

For Part 2 of the study, the change from Week 40 (Baseline for Part 2) to Week 76 (EOT visit for Part 2) in the MDS-UPDRS Part III score will be presented for the early-start and delayed-start K0706 groups. The early-start and delayed-start cohorts will be defined as:

- Early-start the cohort of subjects randomized to K0706 treatment groups in Part 1 (called 'K0706 Pooled' in the summary tables).
- Delayed-start the cohort of subjects randomized to Placebo treatment group in Part 1 and transitioned to K0706 High dose therapy at the beginning of Study Part 2 (called 'Prior Placebo transitioned to K0706 High Dose' in the summary tables).

The above summaries are covered in the first bullet under the Secondary Efficacy Analysis for Part 2.

• Evaluation of slopes of the mean change in MDS-UPDRS Part-III total score over time in Part 2 for the early treatment groups as compared to the delayed treatment group.

The random coefficient regression analyses for Part 2 will be similar to that for Part 1. Note that the prior Placebo group transitioned to K0706 high dose will be used as the reference group for the testing and estimating for the LS mean difference at each time-point during Part-2. Note that the starting time-point for this Part 2 analysis is Part 2's baseline. The same analysis for the Part III total score will be repeated for the analysis of the sum of Parts II and III total scores.

• Proportion of subjects initiating symptomatic treatment.

The difference (and its 90% CI) in the proportion of subjects initiating symptomatic PD medications in Part 2 between each dose of K0706 versus the Prior Placebo transitioned to

K0706 High dose arm will be calculated. In addition, the above statistics will also be presented for the comparison of the early-start group versus delayed-start group.

9.0 SAFETY ANALYSES

All safety data will be summarized for Parts 1 and 2 of the study separately, using the Safety Analysis Set, Part 1 and Safety Analysis Set, Part 2, respectively.

9.1 Adverse Events

All AEs recorded on the eCRF will be coded using the MedDRA dictionary (version 23.0 or a later version if updated during the study) and classified as either pre-treatment AEs or TEAEs for Part 1 or Part 2 of the study as follows:

- Pre-treatment AEs are events that start prior to the start of the Treatment Period.
- TEAEs are either events with start date / time on or after the start of the Treatment Period, or events with start date / time prior to the start of the Treatment Period whose severity worsens on or after the start of the Treatment Period.
- TEAEs for Part 1 of the study are all TEAEs for those subjects not participating in Part 2 of the study and those TEAEs with start date / time before the date of first dose for Part 2 of the study for subjects participating in Part 2 of the study.
- TEAEs for Part 2 of the study are those TEAEs with start date / time on or after the date of first dose for Part 2 of the study.
- Serious TEAEs will be defined as TEAEs regarded by the investigator as Serious = "Yes".
- The relationship between TEAE and study medication is assessed as certainly, probably, possibly, unlikely or unrelated. A study treatment related TEAE will be defined as a TEAE considered by the investigator as certainly, probably, or possibly related to study medication or with missing relationship to study medication.
- Assessment of AE severity will be characterized as mild, moderate, severe, life-threatening and death.
- TEAEs leading to discontinuation of study are defined as TEAEs where "Did AE caused subject to discontinue from the study?" is indicated as "Yes".
- TEAEs leading to discontinuation of study treatment are defined as TEAEs where "Action taken with Study Medication" is indicated as "Drug Discontinued".

AEs will be summarized by default descriptive summary statistics for categorical variables by treatment group and overall, for Parts 1 and 2 of the study separately, using the Safety Analysis Set, Part 1 and Safety Analysis Set, Part 2 respectively, as follows:

• An overview of TEAEs including the number and percentage of subjects with at least one of each mentioned TEAE type:

- Any TEAE
 - Leading to discontinuation of study treatment
 - Leading to death
 - Severity: mild
 - Severity: moderate
 - Severity: severe
 - Severity: life-threatening
 - Severity: death
- Any study treatment-related TEAE
 - Leading to discontinuation of study treatment
 - Leading to death
- Any serious TEAE
 - Leading to discontinuation of study treatment
 - Leading to death
- Any serious study treatment-related TEAE
 - Leading to discontinuation of study treatment
 - Leading to death
- The number and percentage of subjects reporting each TEAE and the count of number of events will be summarized by SOC and PT for the following types of TEAEs:
 - TEAEs
 - TEAEs Leading to Discontinuation of Study Treatment
 - TEAEs Leading to Death
 - TEAEs by Maximum Severity
 - TEAEs by Relationship to Treatment
 - TEAEs by Relationship and Maximum Severity
 - Study Treatment-Related TEAEs
 - Study Treatment-Related TEAEs Leading to Discontinuation of Study Treatment
 - Study Treatment-Related TEAEs Leading to Death

- Serious TEAEs
- Serious TEAEs Leading to Discontinuation of Study Treatment
- Serious TEAEs Leading to Death
- Study Treatment-Related Serious TEAEs
- Study Treatment-Related Serious TEAEs Leading to Discontinuation of Study Treatment
- Study Treatment Related Serious TEAEs Leading to Death
- The number and percentage of subjects who died will be summarized
- The number and percentage of subjects reporting each TEAE and the number of events will be summarized by PT

AEs for Part 1 of the study will be summarized by default descriptive summary statistics for categorical variables by formulation category and overall, using the Safety Analysis Set, Part 1, as follows:

- An overview of TEAEs including the number and percentage of subjects with at least one of each mentioned TEAE type above.
- The number and percentage of subjects reporting each TEAE and the number of events will be summarized by SOC and PT.
- The number and percentage of subjects reporting each TEAE and the count of number of events will be summarized by PT.

In the above summaries, subjects with more than one TEAE within a particular SOC are counted only once for that SOC. Similarly, subjects with more than one TEAE within a particular PT are counted only once for that PT.

For summaries by maximum severity, subjects with multiple TEAEs within a particular SOC or PT will be counted under the category of their most severe TEAE within that SOC or PT. TEAEs with missing severity will be included in the overall count of subjects with TEAEs, but will not be included in the counts of subjects with TEAEs within a SOC or PT.

Summaries by SOCs and PTs will be sorted by SOCs by their Internationally Agreed Order (MedDRA) and PTs within SOC by descending order of total incidence. Where PTs tie, PTs will be sorted alphabetically.

statistical comparisons of AEs between treatment groups will be performed.

All AE data will be listed and Pre-treatment AEs and TEAEs will be presented together. Treatment-emergence status will be flagged in the listing. The listing will present the relative start and stop day of the AE calculated relative to the first dose of treatment and will be presented for those subjects who received at least one dose of study treatment. If the AE is "Ongoing" it will be indicated as such in the listing and the relative stop day will not be calculated. Only original dates will be presented in the listing even though the relative day may be based on an imputed date.

In addition, the following listings will be presented for Parts 1 and 2 of the study separately, using the Safety Analysis Set, Part 1 and Safety Analysis Set, Part 2, respectively:

- Listing of Deaths
- Listing of AEs Leading to Discontinuation of Study Treatment
- Listing of AEs resulting in death
- Listing of Serious AEs

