8.8.2 Post-study Events

Any AE/SAE that occurs up until the follow-up visit, or if the follow-up visit does not occur within the defined time window, then 30 days post the end of treatment visit or 30 days post the last dose of study drug for subjects with early discontinuation, should be reported and included in the safety analysis of the study.

Any AE/SAE which occurs past this date will be reported if it is considered related to study drug by the Investigator.

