9.8 Safety Analyses

The analysis of safety parameters will be based on the Safety Population. In general, missing safety data will be analyzed without imputation or substitution. Treatment-emergent events will be described for Part 1 separately and for Parts 1 and 2 overall. Events will be considered

treatment-emergent if first appearing or worsening following initiation of study therapy and within 4 weeks after study therapy discontinues. See additional details in the SAP.

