4.1.3 Treatment Period

If the time (HH:MM) of data collection is not recorded but the protocol and / or eCRF includes an instruction to the effect that all Day 1 assessments are to be performed prior to the first dose of study drug administration, the data collected at Day 1 will be assigned to the Baseline period. However, adverse events (AEs) and medications starting on Day 1 with missing onset time (HH:MM), will be assigned to the Treatment Period.

The Treatment Period is defined as the period from the date/time of the first dose of study drug administration up to and including the date of the last dose of study drug administration.

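### SAP 9.1 gives treatment-emergent events no end after the last dose, so late events reported only because they were judged related would enter the TEAE tables

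*SAP*

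**What the plan says.** SAP 9.1 sorts every adverse event on the eCRF into one of two classes: "classified as either pre-treatment AEs or TEAEs for Part 1 or Part 2 of the study as follows". Its general rule is "TEAEs are either events with start date / time on or after the start of the Treatment Period", together with earlier events that worsen from then on. The rules for each part add no end after the last dose. For Part 1, "TEAEs for Part 1 of the study are all TEAEs for those subjects not participating in Part 2 of the study"; subjects who do continue have Part 1 closed at their first Part 2 dose. For Part 2, "TEAEs for Part 2 of the study are those TEAEs with start date / time on or after the date of first dose". SAP 4.1.3 closes the Treatment Period, "up to and including the date of the last dose of study drug administration", but the TEAE rule uses only the start of that period.

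Protocol 9.8 counts an event as "treatment-emergent if first appearing or worsening following initiation of study therapy and within 4 weeks after study therapy discontinues" and refers to the SAP for further detail. Two other protocol sections state no end. Section 6.2.3 describes TEAEs only as events after the first dose. Section 9.8.1 asks only whether the event was absent before the first dose or has since worsened.

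On collection, Protocol 8.4 and 8.8.2 gather events of any cause up to the follow-up visit. If that visit misses its window, the limit is 30 days after the end-of-treatment visit, or 30 days after the last dose for early discontinuations. Section 8.8.2 places those events in the safety analysis. It then says: "Any AE/SAE which occurs past this date will be reported if it is considered related to study drug by the Investigator". Protocol 8.6 puts all AEs and SAEs on the eCRF AE form.

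**The concern.** A TEAE percentage is interpretable when every event in its window had the same chance of being recorded, whatever its cause. Here that holds until about a month after the last dose. Beyond that point the trial hears only of events the investigator attributes to the drug. A TEAE definition with no end counts both kinds together. The late events are then treatment-related because relatedness is the condition for reporting them, and unrelated events from the same weeks are missing.

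Two things are at stake. The first is the set of TEAE, treatment-related TEAE and, where the event is serious, serious related TEAE tables in both parts. The second is the Part 2 primary endpoint, which the protocol synopsis gives as TEAE incidence. In Part 2 subjects know they are on active drug, so a late causality judgement there is not made against the possibility of placebo.

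**Working it through.** No figure in the plan needs reproducing, because the point turns on definitions.

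**Step 1. The windows side by side.**

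| Source | Opens | Closes after the last dose |
|---|---|---|
| Protocol 9.8 | start of study therapy | 4 weeks after therapy stops |
| Protocol 9.8.1 | first dose | none stated |
| Protocol 6.2.3 | first dose | none stated |
| SAP 9.1, Part 1, subject not entering Part 2 | first dose | none |
| SAP 9.1, Part 1, subject entering Part 2 | first dose | first Part 2 dose |
| SAP 9.1, Part 2 | first Part 2 dose | none |
| Protocol 8.4 and 8.8.2, collection of any cause | consent | follow-up visit, otherwise 30 days |
| Protocol 8.8.2, collection if judged related | end of the row above | none |

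**Step 2. Which events the SAP counts and Protocol 9.8 does not.**

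- (a) Events of any cause between day 28 and the end of routine collection. Where the 30-day limit runs from the last dose, this is 30 − 28 = 2 days. Where the follow-up visit falls late in its window, the length depends on a visit window that is not legible in the public schedule.
- (b) Events after routine collection ends, which exist in the data only if judged related.

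Only group (b) is selected on causality.

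**Step 3. How group (b) reaches the tables.** Protocol 8.6 puts the event on the eCRF AE form. SAP 9.1 classifies all eCRF events and offers only pre-treatment or TEAE. The onset is after the first dose, so the event is a TEAE. It was reported because it was judged related, so it also counts as treatment-related. This is a chain of two rules; no single sentence states the result.

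**Step 4. Size in Part 1.** The planned total is 506 subjects randomized 1:1:1, so 506 / 3 = 168.7, about 169 per arm. One additional affected subject adds 1 / 169 = 0.6 percentage points to an arm's rate. One to three such subjects (assumed) would add 0.6 to 3 / 169 = 1.8 points. The percentages count subjects, so a subject who already has an event in the same category adds nothing. These figures are therefore upper bounds.

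**Step 5. Size in Part 2.** One subject adds 1/n, where n is the number treated in that group. The documents do not give n. If between all and half of 169 continue (assumed), one subject adds 1 / 169 = 0.6 to 1 / 84.5 = 1.2 points.

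**The case against.** The strongest reply is that the SAP follows one strand of the protocol. Sections 6.2.3 and 9.8.1 have no end either, and 9.8 refers to the SAP for detail. This stands in part: the inconsistency begins in the protocol, and editing the SAP alone would leave it there. It does not remove the point. Section 9.8 is the one place that states an end, and asking the SAP for more detail does not license dropping it. Section 9.8.1 sits under 9.8 and could be read as inheriting its limit, but nothing says so.

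A second reply is that collection closes the window in practice. Someone who stops at Week 8 has a follow-up visit about 4 weeks later (SAP 2.1.1), and routine collection then ends. That also stands, and it is why the effect is small. It leaves the causality-selected reports that follow.

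Third, Protocol 8.8.2 mentions the safety analysis only for events inside the collection limit. Entry of later events into the tables is therefore an inference, though SAP 9.1 provides no other class for them.

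Fourth, late events can be found. SAP 9.1 lists all events with their relative start day, and SAP 9.8 lists last treatment dates. This helps a reader of the listings but does not correct the tables.

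A reader might also infer more than the documents support:

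- **That the excess falls mainly in the arm with more early stops.** The rule covers everyone outside Part 2, including completers who decline it, and the plan gives no dropout by arm.
- **That serious related rates rise by a large fraction.** That needs a base rate the documents do not give, and every late related event would have to be serious.

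**Conclusion.** The point holds as a mismatch of definitions with a small expected effect. Following SAP 9.1 as written would put late events selected on causality into the TEAE and treatment-related TEAE tables, including the table for the Part 2 primary endpoint. The definition bullets in SAP 9.1 read as complete, so blacked-out text does not explain the missing end.

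In Part 1 the effect is at most about 0.6 percentage points per additional affected subject, and zero for a subject already counted. In Part 2 the weight per subject depends on how many continue. The number of late reports and the arm affected are unknown. The conclusion assumes that late related events are entered on the eCRF AE form as Protocol 8.6 requires, and that the programming follows SAP 9.1 literally. The Part 1 efficacy analyses are not affected.

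**What to change.** - **SAP 9.1:** add one post-treatment end to the TEAE definition for both parts, starting from the protocol's 4 weeks after the last dose. Reconcile it with the follow-up-visit or 30-day limit in Protocol 8.4 and 8.8.2. A bare 28-day cut would conflict with 8.8.2, which keeps events up to that limit in the safety analysis. One workable form is 4 weeks, or the end of routine collection where that falls later.
- **Protocol 9.8 and 9.8.1:** state the same end in both. Section 6.2.3 can refer to it.
- **Later-reported events:** show them in a separate post-treatment listing by arm. Keep all deaths and SAEs in their listings regardless of date.
- **Timing:** settle the rule before the Part 1 treatment code is broken.

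The cost is one date condition in the programming, one extra listing, and matching text in the SAP and the protocol sections. The downside is that a few late related events move from the TEAE tables to a listing.

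The change does not equalise off-drug follow-up. Subjects entering Part 2 still have Part 1 closed at their first Part 2 dose, while the others keep about 4 weeks off drug.

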4.3.1 Inclusion Criteria

- 1. Subject has completed part 1 of the study
- 2. Subject projected not to need dopaminergic treatment except for treatment with Monoamine Oxidase B (MAOB) inhibitors. MAOB inhibitors will be allowed if the patient was already taking the same during part 1 of the study.
- 3. Subject has received K0706/placebo within 4 weeks prior to the end of part 1 of the study.

4. Male subjects enrolled in the study should not father a child and are advised to prevent the passage of semen to their sexual partner during intercourse using an effective method, as judged by the Investigator, for the duration of the study and for 3 months after the last dose of study drug.

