7.0 CONCOMITANT MEDICATIONS

It is expected that during the development of the study, the events defined in this section will take place. The aim of this section is to define flags to be created in the efficacy datasets and to facilitate the analysis of the efficacy endpoints as defined in Section 8.

7.1 Start Date of Symptomatic PD Medications for Part 1

The start of symptomatic PD medications will be derived according to the following algorithm:

The symptomatic PD medications will be selected using the following criteria from the WHODrug dictionary: ATC Class Level 2 equals to "ANTI-PARKINSON DRUGS" (Class code: N04).

For subjects on MAO-B inhibitors at baseline, the list of symptomatic PD medications will be the same as the above with the exclusion of the MAO-B inhibitors.

MAO-B inhibitors will be selected from the concomitant medications where ATC Class Level 4 equals to "MONOAMINE OXIDASE B INHIBITORS" (Class code: N04BD).

For subjects on MAO-B inhibitors at baseline, an increase from baseline in daily dose (mg/day) during Part 1 will be considered an intake of symptomatic PD medication as well.

(2) The date (in Part 1) when the first symptomatic PD medications were received or when an increase in the daily dose (mg/day) of MAOB inhibitors happened (whichever was the first occurrence) will be marked as the "symptomatic PD medications start date."

-641 - 6 -- 4 :- 4-1- - - 6 -- -- - 4 :- DD

Protocol Reference: CLR 18 06

(3) All visits or assessments with a date after the date of the first intake of symptomatic PD medication during Part 1 will be marked as "after the start date of symptomatic PD medications".

7.2 Start Date of Symptomatic PD Medications for Part 2

Subjects who started symptomatic PD medications in Part 1 will be withdrawn from the study and cannot enter Part 2. Subjects entering Part 2 are either still naïve to symptomatic PD medications or on MAO-B inhibitors (without an increase in dose) since the Part 1 baseline.

The start of symptomatic PD medications for Part 2 should be after the start of the study drug administration for Part 2. The start date of symptomatic PD medications for Part 2 will be derived and flagged using the same algorithm as above.

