9.7 Prior and Concomitant Medications

All medications will be coded using the World Health Organization (WHO) Drug Global Dictionary, (version Mar 2022 or a later version if updated during the study), Anatomical Therapeutic Chemical (ATC) classification codes.

Prior and concomitant medications are defined as follows:

- Prior medications are those medications with a stop date prior to the start of the Treatment Period.
- Concomitant medications are those with a start date on or after the start of the Treatment Period, or those with a start date before the start of the Treatment Period and either a stop date on or after the start of the Treatment Period, or are ongoing at the end of the study.
- Concomitant medications for Part 1 of the study are all concomitant medications for those subjects not participating in Part 2 of the study and those concomitant medications with start date before the date of first dose for Part 2 of the study for subjects participating in Part 2 of the study.
- Concomitant medications for Part 2 of the study are those concomitant medications with start date on or after the date of first dose for Part 2 of the study.

See Section for imputation of missing or partial dates for medication.

Prior and concomitant medications will be summarized by treatment group and overall for Parts 1 and 2 of the study separately, using the All Randomized Set, Part 1 and All Enrolled Set, Part 2, respectively, as follows:

- The number and percentage of subjects with at least one prior / concomitant medication will be presented.
- The number and percentage of subjects with at least one prior / concomitant medication within each Therapeutic Subgroup (ATC-Level 2), Chemical Subgroup (ATC-Level 4), and PT will be presented. The summary will be sorted using numerical counts by descending order of Therapeutic Subgroup, then descending order of Chemical Subgroup, then descending order of PT in the total column. Where groups or terms tie these will be sorted alphabetically.

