Prior medications will be listed for the All Randomized Set, Part 1. Concomitant medications for Parts 1 and 2 of the study will be listed separately, using the All Randomized Set, Part 1 and All Enrolled Set, Part 2, respectively. In the listings the relative start and stop day of prior / concomitant medication use will be calculated relative to the first dose date of study drug in the corresponding Part period and will be presented for those subjects who received at least one dose of study drug. If the concomitant medication is "Ongoing" it will be indicated as such in the listing and the relative stop day will not be calculated. Only original dates will be presented in the listing even though the relative day may be based on an imputed date.

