12.2 General rules for Statistical Reporting

In general, statistical reporting and analyses will be created separately for Part 1 and Part 2.

The default summary statistics for quantitative variables will be the number of observations (n), mean, SD, median, minimum (min) and maximum (max), for those subjects with data. In addition, geometric mean and CV% of geometric mean will be reported for PK parameters.

All summary statistics will be rounded (using the more decimal place than the raw value, except for the SD and SE values that will be presented to 2 more decimal places than the raw value, and minimum and maximum values that will be presented with the same decimal precision as the raw value. All summary statistics for PK data will be rounded (using the analysis) and presented to 3 significant figures, except for the geometric CV values that will be presented to 1 decimal place.

For qualitative variables, the number (n) and percentage (%) of subjects with non-missing data per category will be the default summary presentation, and where appropriate and present, the number of missing values as a "Missing" category. The number of subjects in the analysis population will be used as denominator for percentages calculation, unless stated otherwise in Tables, Figures and Listings (TFL) mock shell(s).

All statistical comparisons and tests will be performed at the significance level unless specifically stated otherwise.

All central laboratory test results will be provided in International System of Units (SI) and all local laboratory test results will be provided in conventional units.

For the TFL, the results will be summarized or presented in Refer to Appendix of the TLF mock shells for the SI unit corresponding to each laboratory test and the precision level in which each laboratory test is reported by the central laboratory.

Specifications for table, figures and data listing formats can be found in the TFL shells specifications for this study. Please refer to "2. General Format Guidelines" section within TFL shells for more details on presentation of results.

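### SAP 9.7 leaves every drug continued unchanged from Part 1 out of the Part 2 medication outputs; the similar start-date rule in SAP 9.1 may miss events that worsen after the switch, and the both-Parts TEAE summary needs reconciling with Protocol 9.8

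*SAP*

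**What the plan says.** **Medications.** SAP 9.7 opens with a general definition: a drug is concomitant if it starts during treatment, or if it started earlier and was stopped during treatment or is still being taken. Protocol 9.4 likewise includes drugs that carry on into treatment. SAP 9.7 then splits concomitant drugs by Part. Those for Part 2 "are those concomitant medications with start date on or after the date of first dose for Part 2"; a Part 2 participant's earlier starts go to Part 1. On listings it says "Concomitant medications for Parts 1 and 2 of the study will be listed separately". Protocol 4.3.1 says "MAOB inhibitors will be allowed if the patient was already taking the same during part 1 of the study". SAP 7.2 expects subjects to enter Part 2 either free of symptomatic PD drugs "or on MAO-B inhibitors (without an increase in dose) since the Part 1 baseline".

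**Adverse events.** Under SAP 9.1 an event is treatment-emergent if it starts, or worsens in severity, once the Treatment Period has begun. SAP 4.1.3 sets that beginning at the first dose of study drug. TEAEs are then divided between the Parts by start date alone, relative to the first Part 2 dose.

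**Reporting periods.** Protocol 9.8 states: "Treatment-emergent events will be described for Part 1 separately and for Parts 1 and 2 overall". SAP 9.0 states: "All safety data will be summarized for Parts 1 and 2 of the study separately". SAP 9.1 tabulates AEs "by treatment group and overall, for Parts 1 and 2 of the study separately", where overall means across treatment groups. SAP 12.2 adds: "In general, statistical reporting and analyses will be created separately for Part 1 and Part 2".

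**The concern.** The start of Part 2 is a real change point. Prior-placebo subjects receive K0706 for the first time, and TEAE incidence becomes the primary endpoint. Rules that look only at start dates cannot see anything already under way at that moment.

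For medications, this means the Part 2 table reports new starts rather than what subjects were taking. For adverse events, a deterioration on first exposure to K0706 could be credited to the placebo period. Separately, a reader of the protocol would expect a TEAE summary covering the whole study and will not find one in the visible SAP.

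**Working it through.** The documents give no figure to reproduce. The check is to take example records through the SAP rules, with the first Part 2 dose at Week 40.

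**Medications (SAP 9.7)**

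1. An MAO-B inhibitor started before baseline and taken unchanged to Week 76 is not a prior medication, because it did not stop before treatment. It is concomitant under the general definition. Its start precedes the first Part 2 dose, so it goes to Part 1 and is absent from the Part 2 table and listing.
2. Any other drug started in Part 1 and still taken in Part 2 gives the same result.
3. A drug newly started in Part 2, or re-entered with a new start date, appears in Part 2.
4. SAP 9.7 also tabulates the number and percentage of subjects with at least one concomitant medication, for Part 2 in the All Enrolled Set, Part 2. A subject who takes only continued drugs counts there as taking none.

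The omission follows from the rule alone. It depends on no assumption about data collection.

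**Adverse events (SAP 9.1 with 4.1.3)**

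1. Placebo subject, mild event from Week 30, severe at Week 44 on K0706, one record: the start precedes Week 40, so it is a Part 1 placebo TEAE and absent from Part 2 incidence.
2. The same event, with the worsening entered as a new record dated Week 44: counted in Part 2.
3. Event present before the first study dose that first worsens at Week 50, one record: treatment-emergent by worsening, but its start date places it in Part 1.

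Cases 1 and 2 differ only in how worsening is recorded. Protocol 8.4 lists severity as one item per AE, and the visible text does not say whether worsening opens a new record.

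**Scale of the AE point.** Only the planned 506 subjects and the 1:1:1 allocation come from the documents: 506/3 = 168.7 on placebo. The rollover and worsening rates below are assumptions.

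- 60% rollover: 168.7 × 0.60 = 101.2; × 0.02 = 2.0 and × 0.10 = 10.1 subjects.
- 95% rollover: 168.7 × 0.95 = 160.2; × 0.02 = 3.2 and × 0.10 = 16.0 subjects.
- New record opened at worsening: 0 subjects.

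The illustration therefore runs from 0 to 16 prior-placebo subjects. The any-TEAE line would change by fewer, because it moves only for subjects with no other Part 2 TEAE.

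**Reporting periods.** SAP 3.5 defines one safety set per Part and none combining them. The AE tables in SAP 9.1 are by Part, and the formulation tables cover Part 1 only. The general AE listing is not split by Part, but a listing is not a summary.

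**The case against.** *On medications:* continued drugs remain in the Part 1 table and listing, where they can be marked as ongoing. Baseline MAO-B use is tabulated separately (SAP 5.1). Initiation of symptomatic medication in Part 2, which is an endpoint, has its own algorithm in SAP 7.2. All of this stands. A reader might infer that the information is lost or that an efficacy endpoint is affected; neither follows. The Part 2 outputs are still wrong.

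*On adverse events:* the protocol itself attributes by onset. Protocol 8.4 attaches the dose assigned when the event first began, and 9.8.1 plans a summary by actual dose at onset. Keeping an event that began on placebo in Part 1 is consistent with that, so the SAP rule may be deliberate. This stands, and any change must be reconciled with those sections. Three stronger readings are tempting and are not supported:

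- That the SAP contradicts the protocol's definition of treatment-emergent. Protocol 9.8 and 9.8.1 also take the start of therapy as the reference point, so this is a gap in allocation at the switch.
- That such events fall out of both Parts. An event that began during Part 1 treatment already counts in Part 1 incidence; at most its later grade is missing there, if recorded after the Part 1 lock. Only a pre-treatment event that first worsens in Part 2, recorded after that lock and with Part 1 not re-run, could be in neither set of tables. The unsplit AE listing would still show it.
- That 2 to 16 subjects is an estimate of error in the primary endpoint. It rests wholly on assumed rates.

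*On the combined summary:* a reader might infer that the promised table has been dropped. SAP Section 11 and the table shells are not visible, and SAP 12.2 says only that separation is the general practice, so that cannot be established. A pooled table could also blur placebo and K0706 time in prior-placebo subjects.

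**Conclusion.** Three points of unequal strength hold.

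1. **Medications: wrong as written, unconditionally.** SAP 9.7 departs from its own general definition and from Protocol 9.4 in allocating to Part 2. Every drug continued unchanged from Part 1 is missing from the Part 2 table and listing. No endpoint depends on this, but the table does not describe medication use in Part 2.
2. **Adverse events: a conditional gap.** If worsening stays on one record, worsening after the switch is left out of Part 2 TEAE incidence, and for prior-placebo subjects the event is counted under placebo in Part 1. Early-start subjects are subject to the same rule, but their regimen does not change at Week 40, so it matters less for them. The size cannot be derived, and it is zero if worsening opens a new record.
3. **Combined TEAE summary: minor.** Protocol 9.8 and the visible SAP 9.0 and 9.1 do not match and should be reconciled.

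**What to change.** - **SAP 9.7:** count as Part 2 concomitant any medication ongoing at, or started on or after, the first Part 2 dose. This takes one clause, with a re-run of the Part 2 table and listing. Continued drugs will then appear under both Parts.
- **SAP 9.1:** define Part 2 TEAEs as events that start, or worsen in severity, on or after the first Part 2 dose, wherever a new record or a dated grade exists. State which recording convention applies, and reconcile the rule with the onset-based dose attribution in Protocol 8.4 and 9.8.1. The downside is that an event starting in Part 1 and worsening in Part 2 is counted in both Parts, and Part 2 counts may rise slightly. If neither a new record nor a dated grade was collected, the clause cannot be programmed, and the report should state that limit.
- **Protocol 9.8 against SAP 9.0 and 9.1:** add the TEAE summary for Parts 1 and 2 overall, showing prior-placebo subjects so that their placebo and K0706 time are not mixed, or state in the SAP why it is not produced. First check SAP Section 11 and the table shells.

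The total cost is SAP wording, programming and a few tables. No efficacy analysis changes.
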